In order to assess the impact of the programme on the HLE an independent **HLE observation** within the home will be conducted with a sub-sample of participating parents randomly assigned to the intervention condition (30) and the control condition (15) at pre- and post-test (n=45). Whilst to some extent this group will be self-selected (due to the optional nature of this aspect of the study) where possible they will seek to monitor participants across the recruitment phase to ensure they are selected evenly from across the Local Authorities and where possible include a representative sample in terms of quantifiable demographics (e.g. age of parent, socio-economic circumstance, EAL, number of additional children, marital status). This is a novel approach to combining a qualitative outcome assessment from a RCT with a quantified (primary) outcome. Because the outcomes of the intervention are not as tightly defined as in other areas of educational progress (e.g., performance at KS2 or GCSE) observing the parents and children and coding their activity will enable rich and diverse rigorous qualitative findings to be summarised and directly compared with quantified outcomes. The process will involve a 20-minute semi-structured videotaped observation in the home of the parent interacting with their child to assess targeted parenting behaviours. Developed by [name], based on the Play and Reading Observation Tool (PAROT; Pye, 2015) and the Dyadic Parent-Child Interaction Coding Scheme (DPICS; Robinson and Eyberg, 1981) the observation will involve 10-minutes of the parent and child interacting during free-play, followed by 10 minutes of shared book reading. Videos will be coded to form frequency counts to provide an overall assessment of parent-child verbal and non-verbal behaviours relating to the HLE. It is planned to analyse the data to look at potential changes in positive parenting verbalisations (praise, labelling, educational questions) versus more directive, critical verbalisations. For the child, we will look at any potential changes in the overall quantity of verbalisations, as well as the number of verbalisations which are instigated by the child. Coding will be conducted by the Trial Co-ordinator ([name]), trained by [name], who will also conduct the inter-rater reliability checks. Training to be competent in using the observational coding scheme takes place over three full days. Coders are considered competent once they have reached 75% agreement with the primary coder. Inter-rater and intra-rater reliability checks are performed periodically throughout the coding process on a 20% random sample of available videos to ensure coder agreement remains high during dense periods of coding, and to limit coder drift.

A summary of the IPE is provided in Table 2 below.

Table 2: IPE Research Questions and Methods

Research Question	METHOD									
	Routine programme data	Attendance at training	Delivery Team	Face-to-face Site co-ordinators	Interviews Home visitors	Local Authority leads	Parent Telephone interviews	Parent questionnaires	Home Observation	
1. To what extent was the programme implemented as planned?										

 • What training was received and were there any implementer factors in programme delivery? 		X	X	X	X					

 • What was the number and length of sessions delivered? 	X									

 • Any variation in implementation and, if so, why? 			X	X	X					
2. What is the desirability, acceptability and need for the programme within local communities?										

 • Who was the programme was delivered to? 	X	X				X				

 • Were there any parental factors resulting in barriers to, or facilitators of, programme delivery? 	X				X		X	X		

 • Were there any programme factors resulting in barriers to, and facilitators of, programme delivery? 	X		X	X	X		X	X		

 • What was usual parenting practice in the absence of the programme? How did this change as a result of taking the ParentChild+ programme? Were there any changes as a result of being in the control condition? 						X	X	X		

Research Question	Routine programme data	Attendance at training	METHOD				Parent Telephone interviews	Parent questionnaires	Home Observation
			Face-to-face Interviews	Delivery Team	Site co-ordinators	Home visitors			
3. To what extent did the ParentChild+ programme impact on the HLE, particularly on parent-child verbal interactions?									X
4. What were the wider outcomes of the programme?									
• What was the impact in terms of parental confidence and efficacy?							X	X	
• To what extent did participation result in parents taking up the free nursery offer?					X	X	X	X	
• To what extent did the programme result in increased parent engagement with wider community services?				X	X		X	X	
• Were there any diffusion effects of programme delivery?					X		X	X	

ANALYSIS

Process evaluation data will be (where applicable):

- Transcribed and coded in NVivo using pre-agreed 'parent codes' relating to the logic model and the IPE research questions (Local Authority leads, Delivery Team, site coordinators, home visitor and parent interviews). 'Child codes' will subsequently be developed within these to provide relevant detail focused on participants' experiences and views;
- Checked to ensure at least 75% inter-rater reliability on a sub-sample (N = 20% of all videotaped observations) of records (where coded);
- Inputted twice and checked for quality assurance purposes (routinely-collected data and bespoke parent questionnaire)

Analysis will be triangulated to provide a fuller picture of the implementation of the programme from the point of view of all stakeholders.

Cost evaluation

As per EEF guidelines, the evaluation team will provide a cost per child for the intervention (approximately 15 months), and include detail regarding dosage of the programme received over this time period. These costs will include home visitor recruitment and training (including any subsequent additional recruitment and training over the period of the trial), travel costs and provision of materials. We will use this data to estimate the costs of continuing to roll the programme over a three year period. Additional costs of implementation will be systematically identified in the process evaluation. Cost implications will be identified according to current EEF guidelines through discussions with the Delivery Team and home visitor feedback.

Ethics and registration

Ethical approval for this study will be sought through the Education Ethics Committees, University of York, Durham University and Leeds Beckett University. We will also comply with any ethical approval processes required by the participating Local Authorities.

All outputs (including the statistical database, reports and publications) will be anonymised. No participant or setting will be identifiable in the report or dissemination of results. The statistical database will hold non-identifiable data.

Five per cent (5%) of the assessments will be randomly selected and double-checked, to assess reliability and consistency. All scores will be input twice to ensure accuracy. Confidentiality will be maintained and no one outside of the evaluation team will have access to the database which will be held securely on the department servers. Full consent will be obtained from parent/carer participants including depositing data at the end of the trial and the possibility of linking to the NPD to conduct follow-up analysis. Given that visits by data collectors will take place in the home, we have in place SOPs to ensure researcher safeguarding.

The trial will be registered with the ISTRCN.

Data protection

Data will be handled in accordance with the General Data Protection Regulations (GDPR). Personal data will be processed under Article 6 Section (e) of the GDPR ('Tasks carried out in the public interest') as the research is being conducted to support education provision in the UK (and, if applicable, Special Category data under Article 9(2)(j)). A Data Protection Impact Assessment (DPIA) has been conducted (approved by Data Protection officer, University of York, 24/04/2019) and Data Sharing Agreements will be put in place with the University of York, Family Lives and the participating Local Authorities.

Personnel

The Evaluation Team is responsible for the conduct of the evaluation, including writing the protocol and SAP, registering the trial, writing consents, data sharing agreements and privacy notices and gaining ethical approval, data collection, analysis and writing the final report.

The Evaluation Team comprises:

[name] (Co-PI). [name] will be responsible for the day-to-day management and coordination of the trial, working closely with the programme developers and supervising the trial co-ordinator. She will lead on the protocol and the report writing and contribute to the Implementation and Process Evaluation (IPE).

[name] (Co-PI). [name] will work closely with [name] to design the trial, including the unique approach to providing blinded impact and process outcomes and provide overall quality assurance and expertise in mitigating any potential biases and their risks, having had experience in dealing with both in past evaluations. She will contribute to the report writing and the IPE.

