Trial Evaluation Protocol

ParentChild+

Evaluator: University of York & Durham University

Principal investigator(s): [name] & [name]

PROJECT TITLE	Efficacy Trial of the ParentChild+ programme
DEVELOPER (INSTITUTION)	Family Lives
EVALUATOR (INSTITUTION)	University of York, Durham University & Leeds Beckett University
PRINCIPAL INVESTIGATOR(S)	[name] & [name]
PROTOCOL AUTHOR(S)	[name], [name], [name], [name], [name] & [name]
TRIAL DESIGN	Two-arm within-local authority RCT with randomisation at the family level
CHILD AGE RANGE	2-3 years of age
NUMBER OF LOCAL AUTHORITIES	4
NUMBER OF CHILDREN	320
PRIMARY OUTCOME	British Picture Vocabulary Scale (BPVS-III; Dunn, Dunn and NfER, 2009) (Receptive Vocabulary)
SECONDARY OUTCOMES	
 • Communication, personal-social skills and fine motor skills sub-sections of the Ages & Stages Questionnaire (ASQ-3; Squires and Bricker, 2009) • Home Learning Environment (HLE) Index (Melhuish, 2010) • School attainment as recorded in the National Pupil Database (NPD) eg. Reception Baseline Assessment (RBA), EYFS Profile

Protocol version history

VERSION	DATE	REASON FOR REVISION
1.0 [original]	11/09/2019	

Table of contents

Intervention.....	3
Study rationale and background	3
Impact Evaluation.....	5
Research questions	5
Design	5
Randomisation	6
Participants	6
Incentives for participating parents	7
Sample size calculations	8
Outcome measures.....	8
Analysis plan.....	9
Implementation and process evaluation	12
Cost evaluation	18
Ethics and registration.....	18
Data protection	19
Personnel	19
Risks.....	20
Timeline.....	23
References	24
Appendix: ParentChild+ Evaluation Flow chart.....	26

Intervention

An intensive home visiting programme developed in the US in the 1960s, ParentChild+ (previously the Parent-Child Home Programme) aims to increase parent-child interaction, promote positive behaviours and encourage language and other emerging literacy skills to enhance the home learning environment, promote school readiness and foster academic success. It is a targeted-selective programme primarily aimed at low income families with children aged 2-3 years of age. It is delivered in the home by specially trained home visitors over a 15 month period. It models positive parent-child interaction using age appropriate books and toys which are then gifted to programme participants.

Table 1: TIDieR

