Sample size calculations were conducted using Stata v15.0. Although the unit of randomisation will be households, in the vast majority of these there will be only one eligible child. Therefore the sample size has been conducted as for an individually randomised trial. Multiple eligible children within a household will be allowed to take part, and in these cases we will use the mean of the scores obtained within the household for statistical analyses. The DT have estimated that they would have capacity to support 160 families in the intervention (40 in each of 4 geographical regions). Using equal randomisation, we aim to recruit 320 families. Assuming scores obtained at baseline and follow up are approximately bivariate normal with a correlation of 0.7 and 20% attrition at follow up (n=64), this sample size (n=256) gives a minimum detectable effect size (MDES) of 0.25 in a two-sided test of the difference between groups adjusted for baseline with nominal type 1 and 2 error rates of 5% (i.e. alpha of 0.05) and 20% (i.e. power of 80%), respectively. This would mean that this study would be able to detect lower effect sizes than those in the US studies discussed above.

Outcome measures

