analysed according to the group they were assigned to (either intervention or control) regardless of adherence to that condition or not (i.e. participants allocated to receive the intervention will be analysed within the intervention group even if they do not participate in the programme). Where participants withdraw from the programme this shall not be classed as withdrawal from the study and participants will be asked to continue participating in the data collection and data processing aspects of the study. Baseline data will be summarised descriptively, both as randomised and as included in the primary analysis, with no formal comparisons being undertaken. Both adjusted and unadjusted summaries of the outcome measures will be presented, with p-values and appropriate 95% confidence intervals (CI) given for all between group comparisons.

A CONSORT diagram will be produced to show the flow of households and participants through the trial.

Primary Analysis

Linear regression will be used to compare raw BPVS-III scores between the two groups. Group allocation, baseline (raw) BPVS-III score, age and Local Authority will be included as fixed effects in the model. Participants with either age missing or baseline BPVS-III score missing will have these imputed with the relevant strata specific mean. Hence all participants with non-missing BPVS-III scores at follow up will be included, as randomised, in the primary analysis model. The BPVS-III is a norm-referenced test and standardised for children aged 3 years to 16 years and 11 months. However the children being recruited as part of this trial will all be less than three years old at baseline, meaning no age standardised scores exist. Hence the inclusion of age as a covariate. The inclusion of age as a covariate is also likely to increase the precision of the estimate of the treatment effect. Inferences regarding the effectiveness of the ParentChild+ programme will be based on the adjusted difference in mean score between the two groups suggested by this model. Effect size will be summarised using Hedges' g and associated 95% CI.

Further analyses of primary outcome

Further analyses of the primary outcome will be conducted to investigate the possible influence of non-compliance on the result of the primary analysis, and to assess the sensitivity of the primary analysis to variation in the missing data assumptions.

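### The MDES of 0.25 and the primary regression assume independent intervention families and make no allowance for families sharing a home visitor

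*Protocol*

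**What the plan says.** The protocol's Sample size calculations section observes that nearly all households will have one eligible child, handles the exceptions by averaging scores within the household, and concludes: "Therefore the sample size has been conducted as for an individually randomised trial". Its target is set by delivery capacity, "capacity to support 160 families in the intervention (40 in each of 4 geographical regions"), and it continues: "Using equal randomisation, we aim to recruit 320 families". Scores are taken to be "approximately bivariate normal with a correlation of 0.7 and 20% attrition at follow up (n=64), this sample size (n=256"), which "gives a minimum detectable effect size (MDES) of 0.25 in a two-sided test of the difference between groups adjusted for baseline", at "nominal type 1 and 2 error rates of 5% (i.e. alpha of 0.05) and 20% (i.e. power of 80%), respectively". The section adds that the trial could therefore detect effects smaller than those of the US studies; the background section gives 0.318 for receptive vocabulary.

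On delivery, the Intervention section says: "It is delivered in the home by specially trained home visitors over a 15 month period". Table 1 (TIDieR) describes one visitor working with one parent-child pair, twice a week, for 92 visits.

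On analysis, the Primary Analysis section says: "Linear regression will be used to compare raw BPVS-III scores between the two groups". The fixed effects are allocation, baseline score, age and Local Authority. The further analyses of the primary outcome address non-compliance and missing data. No part of the sample size or primary analysis text mentions home visitors.

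**The concern.** Randomising by household removes clustering at allocation, but delivery can bring it back in one arm. If some visitors achieve more than others, families with the same visitor share that part of the outcome. The intervention arm then carries less information than 128 independent families, while controls, who have no visitor, are unaffected. This is a partially nested design. The protocol's reason for ignoring clustering, one child per household, does not bear on it. The Local Authority term absorbs differences between areas but not between visitors within an area.

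The protocol itself treats visitors as a possible source of variation. The process evaluation asks about implementer factors and the visitor-parent relationship, and uses a graded rating of delivery.

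At stake are the stated sensitivity of the trial and the width of the primary confidence interval. There is also a practical deadline. The routine programme data listed under Methods are sessions completed, withdrawals and reasons for cancelled visits. Visitor identity is not listed, and if it is not captured during delivery, no later analysis can use it.

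**Working it through.** **Inputs from the protocol.** 320 families, 1:1, 20% attrition, so 256 analysed and n = 128 per arm; correlation r = 0.7; two-sided 5%; 80% power.

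**Assumed inputs, because the protocol gives none.** Recruited families per visitor: 5, 10 or 16, which after 20% attrition leaves m = 4, 8 or 12.8 analysed. Visitor ICC of the baseline-adjusted residual: 0.01, 0.05 or 0.10.

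**Are visitors shared?** With 40 families per area and two visits a week, a full area needs 40 × 2 = 80 visits a week. One visitor per family would mean 160 trained visitors. The interview plan calls one visitor per area a sample, so each area has more than one. Several families per visitor is a safe inference, though not a stated fact.

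**The protocol's own figure.** Residual SD = √(1 − 0.7²) = √0.51 = 0.714.
MDES = (1.960 + 0.842) × 0.714 × √(2/128) = 2.802 × 0.714 × 0.125 = 0.2501.
The stated 0.25 reproduces, so there is no arithmetic error.

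**With visitor clustering in the intervention arm only.**
Arm variance inflation: V = 1 + (m − 1) × ICC.
Design effect for the difference: D = (1 + V)/2.
MDES = 0.2501 × √D.
Type I error of the unadjusted test = 2 × [1 − Φ(1.96/√D)].

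Middle case, m = 8 and ICC 0.05: V = 1 + 7 × 0.05 = 1.35; D = 1.175; √D = 1.084.
- MDES = 0.2501 × 1.084 = 0.271.
- SE = 0.714 × √(2.35/128) = 0.0968; power at 0.25 = Φ(0.25/0.0968 − 1.96) = 0.734.
- Type I error = 2 × [1 − Φ(1.808)] = 0.071.

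Each cell gives MDES / power at 0.25 / type I error:

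| Recruited (analysed) per visitor | ICC 0.01 | ICC 0.05 | ICC 0.10 |
|---|---|---|---|
| 5 (4) | 0.252 / 79.4% / 5.2% | 0.259 / 77.1% / 5.9% | 0.268 / 74.3% / 6.8% |
| 10 (8) | 0.254 / 78.6% / 5.4% | 0.271 / 73.4% / 7.1% | 0.291 / 67.4% / 9.2% |
| 16 (12.8) | 0.257 / 77.7% / 5.7% | 0.285 / 69.2% / 8.5% | 0.315 / 60.3% / 12.0% |

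These use the normal approximation, as in the reproduction of 0.25. With approximate Satterthwaite degrees of freedom the middle case becomes 0.277 and the worst corner 0.333.

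**What the type I figures depend on.** A simulation with 128 per arm, 16 visitors and an ICC of 0.05 (visitor number and ICC assumed) separates three situations. When visitors have random effects averaging zero, the ordinary test rejects about 7% of the time. When the same ICC arises only from how families are sorted to visitors, it rejects about 5%. When the visitor effects are fixed with mean zero, so that inference is to these visitors only, it rejects slightly less than 5%.

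**The case against.** A reader might infer that 0.25 is wrong, that 80% power is not delivered and that the primary model is invalid. The protocol does not support that reading. Visitor number, caseload and ICC are all absent, and at ICC 0.01 with small caseloads the MDES still rounds to 0.25.

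Nor does the protocol say that one visitor stays with a family throughout. Two visitors attend where there are safeguarding issues, and the Risks section rates visitor turnover as a medium risk. Both would blur clustering by a single visitor.

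The background section also describes cultural and linguistic matching of visitors to the communities served. Within-visitor correlation may then partly reflect which families a visitor was given. That part is already in the ordinary residual variance of an individually randomised trial and needs no inflation, so a visitor random effect could over-correct. Further, if the programme affects nobody, visitors create no correlation. In a trial labelled efficacy, inference limited to the visitors employed is also defensible. Lastly, analysis detail is deferred to a SAP that is not at hand.

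Most of this stands. It makes the size of the problem conditional, and it means that replacing the primary model is a choice on which reasonable statisticians could differ. It does not rescue the stated rationale, which addresses households only. The MDES is stated without qualification in the protocol, and a visitor term added in the SAP would still need visitor identity to have been collected.

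**Conclusion.** The point holds conditionally. The MDES and the primary regression both assume independent intervention families, and the reason given does not cover shared visitors. If visitors differ in effectiveness, 0.25 is optimistic, and the standard error is too small for conclusions meant to reach beyond the visitors used: the correct one is 1.01 to 1.26 times as large over the assumed range. The MDES over that range is 0.252 to 0.315, with 0.271 in the middle case. At ICC 0, or if the correlation is only case mix, 0.25 and the 5% level stand.

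The claim that the trial can detect effects below the US 0.318 survives over this range on the protocol's own normal-approximation basis. It is tight in the corner of 16 recruited families and ICC 0.10, where small-sample degrees of freedom give 0.333. All of these sizes rest on the assumed caseload and ICC, and should be replaced once the delivery team's figures are known.

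**What to change.** 1. Add home-visitor identity, for each visit, to the routine programme data. Visit-level recording copes with turnover and paired visits better than a single main-visitor label.
2. State the planned number of visitors and the caseload.
3. State that 0.25 assumes no visitor clustering, and show the MDES over the full ICC range (0.252 to 0.315 under the assumptions here), not only its favourable part.
4. Pre-specify, at least as a sensitivity analysis of the primary outcome, a partially nested model: a random visitor effect in the intervention arm only, controls as singletons, arm-specific residual variance and small-sample degrees of freedom. Say whether inference is meant for these visitors or for visitors in general, and how matching of families to visitors affects the reading of the variance component.

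The cost is one data field, some text and one further model; no extra families are needed. Intervals from that model will be slightly wider, and the visitor variance will be imprecisely estimated if visitors are few or change during delivery.

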This is a two-arm efficacy RCT with allocation at family level to evaluate this intervention against usual care, with an embedded implementation and process evaluation. As ParentChild+ is currently being piloted in the UK it seems reasonable to move to the next stage of evaluation using an efficacy trial design.

Trial type and number of arms	Two-armed, efficacy trial, randomised within local authority.
Unit of randomisation	Family-level
Stratification variables	Local Authority
Primary outcome	Variable
	measure (instrument, scale)
	BPVS-III
	variable(s)
	Communication skills

Secondary outcome(s)	measure(s) (instrument, scale)	Communication subscale of the Ages & Stages Questionnaire (ASQ)
	variable(s)	Personal-social skills
	measure(s) (instrument, scale)	Personal-social skills subscale of the ASQ
	variable(s)	Fine motor skills
	measure(s) (instrument, scale)	Fine motor skills subscale of the ASQ
	variable(s)	Home Learning Environment (HLE)
	measure(s) (instrument, scale)	Home Learning Environment (HLE) Index
	variable(s)	Educational attainment
	measure(s) (instrument, scale)	National Pupil Database (Reception Baseline Assessment (RBA), Early Years Foundation Stage profile (EYFS))

Randomisation

Once parents have consented to participate and all baseline testing has been completed, the household will be randomly allocated 1:1 to receive either the intervention or business as usual. Stratified block randomisation will be used with variable block sizes, by Local Authority (Barnsley, Doncaster, Sheffield and Rotherham). An independent trial statistician at the York Trials Unit will be responsible for generating the allocation schedule. As rolling recruitment is to be conducted the names of participants will be sent to the statistician in possession of the allocation schedule in batches on a regular basis. The names will then be placed in a random order (within each stratum) and matched against the next available allocations. The allocations will then be communicated to the participants and the delivery team will be sent a list of those participants allocated to the intervention. Local Authorities will also be informed of study and programme participants after randomisation under an arrangement whereby programme participation will be accepted by the Department for Education in lieu of take-up of free 2 year old nursery places. This does, however, mean that local authorities will not be blind to condition.

Participants

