The primary child outcome will be the **British Picture Vocabulary Scale** (BPVS-III; Dunn, Dunn and NfER, 2009) administered one-to-one by independent assessors blind to condition, trained and organised by the University of York. The BPVS-III is a standardised measure of receptive vocabulary based upon the Peabody Picture Vocabulary Test (PPVT: Dunn and Dunn, 1981) which has been used in a number of US evaluations of ParentChild+. The basic testing activity involves showing the child a series of images, four to a page, one of which will match a pre-specified word the assessors says to the child. The child is required to point to the picture they believe most closely resembles the word given. It takes between 5 and 8 minutes to administer. As no reading or verbal response is required it is considered suitable for young children and those for whom English is an Additional Language. It is also easy to administer and takes a relatively short time to complete enabling children to remain focused during the assessment period. The BPVT-III has proven to be highly correlated with later literacy acquisition (Dunn, Dunn and NfER, 2009). It is standardised for children aged 3 to 16 years, but can also be administered to two year olds. The previous version of the BPVS (BPVS-II) was standardised for two and a half year old children. Consequently we expect it to be suitable to be administered to two-year-olds but we will pilot the BPVS-III prior to its use to confirm its suitability for this study. The pilot will take place with 10-15 children aged between 18 months and three years of age recruited from nurseries and local parent- and play-groups in order to confirm that there is no floor effect. We will aim to have a mixture of children for whom English is an Additional Language and who are eligible for the two-year old free nursery places. The measure will be regarded as suitable providing there is variation in response and no floor effects are detected. Assuming its suitability, the BPVS-III will form the primary pre-test and be administered by data collectors from the University of York prior to randomisation.

The secondary outcomes are:

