The responses to the 16 items of the Home Learning Environment Index will be combined to give an overall score, with higher scores being indicative of a more positive home learning environment. This score will be analysed using a linear regression model adjusting for allocation, baseline score and local authority. Any missing baseline scores will be imputed with the strata specific mean prior to analysis. Hence all participants with a non-missing Home Learning Environment Index score at follow up will be included in the model.

Subgroup Analyses

Three pre-specified exploratory analyses of the primary outcome will be conducted to investigate the possibility of treatment effect heterogeneity among trial participants. Variation in treatment effect will be explored across different levels of the following three baseline characteristics; Children in Need status, (a binary classification of whether or not the child has ever been a “Child in Need” at any time in their life up until baseline), English as an Additional Language (again a binary classification) and baseline score on the ASQ communication subscale. Baseline score for the ASQ will be used for this subgroup analysis because, unlike the BPVS-III, it is age standardised for children as young as 1 month, and therefore appropriate for the developmental stage of participating children at baseline. The communication subscale will be used as it aligns more closely with the construct measured by the BPVS-III than either of the other two ASQ scales that are being collected.

In all three cases treatment effect heterogeneity will be investigated by examining whether or not the inclusion of the main effect (if not already present), and its interaction with randomised group, in the model used for the primary analysis leads to a significant improvement in model fit. If the inclusion of such interactions does lead to improved model fit, then this model will be used to assess between group differences within strata and provide associated inference.

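### Two collected baseline variables, ASQ communication and EAL status, are left out of the primary BPVS-III model; adding them costs about 2 df and could partly offset a baseline correlation below the assumed 0.7

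*Protocol*

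**What the plan says.** **Model.** The Primary Analysis section compares raw BPVS-III scores by linear regression: "Group allocation, baseline (raw) BPVS-III score, age and Local Authority will be included as fixed effects in the model". It notes that all children will be under three at baseline, where the test has no norms. It gives this as the reason for adding age, and expects age to improve precision as well. Missing age or baseline BPVS-III is filled with the stratum mean.

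**Other baseline data.** The ASQ is completed at pre-test (Outcome measures). The Subgroup Analyses section prefers ASQ communication to BPVS-III as a baseline subgroup variable because "unlike the BPVS-III, it is age standardised for children as young as 1 month, and therefore appropriate for the developmental stage of participating children", and because it lies closer to what BPVS-III measures than the other two ASQ scales collected. EAL is another of the three subgroup variables.

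**Sample size.** "Using equal randomisation, we aim to recruit 320 families". Baseline and follow-up scores are assumed to be "approximately bivariate normal with a correlation of 0.7 and 20% attrition at follow up (n=64"), and "this sample size (n=256) gives a minimum detectable effect size (MDES) of 0.25 in a two-sided test". No source is given for 0.7. The section concludes that the trial could detect effects smaller than those in the US studies. The Study rationale section gives these as 0.318 for receptive vocabulary and 0.372 for language scores.

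**Pilot.** On the suitability of BPVS-III at this age: "The pilot will take place with 10-15 children aged between 18 months and three years of age". The criteria are variation in response and no floor effect.

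**The concern.** The detectable effect depends entirely on how well baseline BPVS-III predicts the follow-up score. A floor effect or poor reliability at age two would lower that correlation, and nothing in the protocol estimates it: the pilot looks at spread and floor only. Meanwhile the protocol collects another baseline language measure, which it regards as suited to this age, and a language-background variable. It uses neither as a covariate in the primary model. The protocol already accepts precision as a reason to adjust for age, and the same reasoning extends to these two. At stake is precision that may be available from data already collected.

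**Working it through.** **Inputs from the protocol.** Recruited 320, attrition 20%, so analysed N = 320 × 0.8 = 256. Allocation: "the household will be randomly allocated 1:1". Error rates: "nominal type 1 and 2 error rates of 5% (i.e. alpha of 0.05) and 20% (i.e. power of 80%), respectively", two-sided. Correlation r = 0.7.

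**Input not in the protocol (assumption).** The joint partial correlation p of ASQ communication and EAL with follow-up BPVS-III, given the covariates already in the model. I use 0.2 to 0.4.

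**Step 1: reproduce the stated figure.**
MDES = (1.960 + 0.842) × √(1 − r²) × 2/√N
= 2.802 × √0.51 × 2/16 = 0.2501.
The stated 0.25 reproduces. With a t distribution on 249 df (256 less 7 parameters: intercept, arm, baseline, age, three for Local Authority) it is 0.251.

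**Step 2: vary r, with N fixed at 256.**

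| r | MDES | Power at 0.25 |
|---|---|---|
| 0.7 | 0.250 | 80.0% |
| 0.6 | 0.280 | 70.5% |
| 0.5 | 0.303 | 63.7% |
| 0.4 | 0.321 | 58.8% |

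These figures give no credit for age and Local Authority, so they are somewhat pessimistic if those two predict outcome beyond baseline BPVS-III.

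**Step 3: compare with the US effects.** Setting the MDES to 0.318 gives √(1 − r²) = 0.318/0.3502 = 0.908, so r = 0.42. At r = 0 the MDES is 0.350, still below 0.372.

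**Step 4: add the covariates.** Residual variance is multiplied by (1 − p²), so the MDES is multiplied by √(1 − p²): 0.980 at p = 0.2, 0.954 at p = 0.3 and 0.917 at p = 0.4.

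| r | MDES without | p = 0.2 | p = 0.3 | p = 0.4 |
|---|---|---|---|---|
| 0.7 | 0.250 | 0.245 | 0.239 | 0.229 |
| 0.6 | 0.280 | 0.274 | 0.267 | 0.257 |
| 0.5 | 0.303 | 0.297 | 0.289 | 0.278 |
| 0.4 | 0.321 | 0.314 | 0.306 | 0.294 |

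**Step 5: what full recovery would take.** To return to 0.25, p = √((0.49 − r²)/(1 − r²)). This is √(0.13/0.64) = 0.45 at r = 0.6 and √(0.24/0.75) = 0.57 at r = 0.5.

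**Step 6: price if the covariates predict nothing.** About 2/249 = 0.8% in variance, or 0.4% in the MDES (0.250 to 0.251).

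**The case against.** The strongest reply is that nothing here is wrong. The MDES reproduces, and adjusting for the baseline of the outcome, age and the stratification factor is a valid, standard model. Further detail is left to a statistical analysis plan that is not shown. This stands as a defence against any charge of error. It does not remove the point, because the protocol itself lists the model's covariates and omits these two.

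Several stronger readings are tempting, and the document does not support them.

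- *Without norms, baseline BPVS-III is a poor covariate.* A reader might infer this, but a raw score can predict well in a model that also contains age, which is how the protocol deals with the missing norms. The remark preferring the ASQ explains the choice of subgroup variable. It says only that the communication scale is closer to BPVS-III than two other ASQ scales are.
- *The ASQ is otherwise unused.* Its three scales are secondary outcomes, each adjusted for its own baseline. ASQ communication and EAL could also enter a sensitivity refit of the primary model if they predict missingness.
- *The pilot cannot reveal a floor.* If 10% of children were at floor, a pilot of 10 to 15 would show none with probability 0.9^10 = 35% to 0.9^15 = 21%. At 30% the probability is only 0.7^10 = 2.8% to 0.7^15 = 0.5%, so a serious floor would probably be seen. The pilot also includes children as young as 18 months, recruits from parent- and play-groups as well as nurseries, and aims for a mix that includes EAL children and those eligible for free places. What it does not do is estimate the correlation.
- *The two covariates would secure the 0.25.* The document gives no correlation of either with follow-up BPVS-III, and step 5 shows that full recovery needs large partial correlations.

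**Conclusion.** The point holds as a low-cost improvement to the primary model, not as an error in the sample size. The 0.25 is correct given r = 0.7, but that value is unsourced, and the MDES rises to 0.303 at r = 0.5. Adding ASQ communication and EAL could recover part of such a loss: to 0.297-0.278 at r = 0.5, with the MDES falling to 0.245-0.229 if r = 0.7 is right. Both ranges rest on the assumed partial correlations of 0.2 to 0.4. If the covariates turn out not to be prognostic, the loss is negligible.

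A reader might infer that the comparison with the US studies collapses. It does not. At r = 0.5 the MDES is still below 0.318, the comparison with that effect fails only below r of about 0.42, and the comparison with 0.372 survives at any correlation. The range of MDES is a supporting clarification only.

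**What to change.** Before outcome data are seen, by protocol amendment or in the statistical analysis plan:

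- Add baseline ASQ communication score and EAL status to the covariates of the primary model.
- Extend the missing-baseline rule to both, so that every child with a follow-up BPVS-III score stays in the model. The stratum mean can serve for the ASQ score. EAL is binary, so use a missing category or indicator, because a stratum mean would give a fraction.
- In the sample size section, show the MDES over r = 0.5 to 0.7 (0.30 to 0.25), and say that the comparison with the US effect of 0.318 requires r above about 0.42.

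The cost is about 2 df (one more if EAL needs a missing indicator), a few lines of text, and a less favourable but more informative MDES statement. No new data are needed. The subgroup procedure already allows for a main effect that is in the model, so it needs no rewriting.
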